Inclusion Criteria	 ALL SUBJECTS: Subjects must be able to understand and provide written informed consent Age 18 to ≤40 years of age, any gender, any racial/ethnic origin. Participant must be willing to comply with study procedures and requirements. Participant must be considered eligible for participation based on results of screening procedures conducted by protocol number 20100686 at VCU and IRB# 12656 at UVA.
	Subjects with asthma
	Criteria for inclusion will include those:
	• with physician-diagnosed, mild asthma who are only using bronchodilators (e.g. albuterol) for symptom control.
	 Asthma Control Test (ACT) Questionnaire Score a > 19 at enrollment before the inoculation with RV-16 (See Appendix: Asthma Control Test).
	 Short-acting beta-agonist use < daily in last 4 weeks FEV1 > 70%, or FEV1/FVC ratio > 75% for subjects with FVC values between 80 and 87% predicted whose FEV1 values fall below 70%. a positive methacholine challenge test (i.e. at least a 20% fall in FEV1) at a methacholine concentration of 16 mg/ml or less (15). The methacholine test will not be done if subjects have used albuterol within 4 hours of the test procedure. Evidence for atopy demonstrated during screening (under IRB protocol# 12656) as judged by positive prick skin tests to one or more aero-allergens.
	Control subjects. Criteria for inclusion will include those who do not have a history of asthma or allergic disorders (e.g. allergic rhinitis, atopic dermatitis, or food allergies).
Exclusion Criteria	 ALL SUBJECTS: Inability or unwillingness of a participant or subject's legal representative to give written informed consent and HIPPA authorization Positive test for serum neutralizing antibody to RV-16. Subjects with a neutralizing antibody titer ≥ 1:4 will be excluded. Chronic heart disease, lung diseases other than asthma, or other chronic illnesses, including primary and/or secondary immunodeficiency. An upper or lower respiratory tract infection within six weeks prior to enrollment

Page 5 of 50

- Who have required nasal or sinus surgery, excluding surgery for a deviated septum within 12 months prior to enrollment.
- Who have a 5 pack/year history of smoking, or any smoking within the last 6 months.
- Female subjects who are or who plan to become pregnant during the study, or who are
 nursing a baby. Additionally, to be included in this study, a woman of child-bearing
 potential must have a negative urine pregnancy test at screening, during the run-in, and

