 prior to viral inoculation and agree to use an effective method of birth control such as, but
 not limited to, birth control pills, contraceptive foam, diaphragm, IUD, abstinence, or
 condoms.
- Absolute neutrophil count (ANC) < 1500 cells/mm3 (or 1.5 K/uL) detected during screening within 6 weeks of enrollment.

Subjects with asthma

Criteria for exclusion will include those:

- Who have required inhaled steroids (used for asthma), nasal steroids (used for allergic rhinitis), cromolyn, nedocromil sodium, ipratropium bromide, or leukotriene modifiers during the month prior to enrollment, oral steroids within 6 weeks of enrollment, omalizumab (Xolair®) within 6 months prior to enrollment, or who are currently using beta adrenergic blocking agents.
- Who have been hospitalized or treated in the emergency room (unless the treatment involved the use of a bronchodilator only) for asthma within the last three years.
- To avoid RV-16 inoculations in subjects with more restrictive lung volumes, those whose FVC is < 80% predicted will be excluded. Subjects who are currently receiving allergen immunotherapy (IT), or who have received allergen IT within the last 3 years. Subjects who have had one or more night time awakenings caused by asthma symptoms and/or who have needed their SABA (albuterol) inhaler for asthma symptoms \geq 4 days during the week before enrollment, or during the week before the inoculation with RV-16.

Control subjects

• Who have a positive methacholine test, or positive prick skin tests at screening under IRB protocol # 12656.

Investigational Product(s)/Intervention(s)

All subjects will receive Rhinovirus 16 challenge IND# 15162

Study Procedures

The following procedures will be performed in this sub-study:

- Medical and allergy history
- Limited physical exam
- Urine pregnancy test/Urine LTE4
- Nasal wash
- Monitoring of nasal mucous and secretion weights during the first 4 days of the infection
- Skin testing, including tests for Alternaria, dust mite, and ragweed, grass and tree pollen allergens
- Spirometry
- Exhaled Nitric Oxide

Page 6 of 50

	CBC/differential	
	Serum IgE levels (total and allergen specific)	
	T-cells blood test	
	RV 16 antibody titers by neutralization assay	
	Methacholine challenge	
	Impulse oscillometry	
	RV 16 inoculation	
	Completion of diary cards	

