- Who have required inhaled steroids (used for asthma), nasal steroids (used for allergic rhinitis), cromolyn, nedocromil sodium, ipratropium bromide, or leukotriene modifiers during the month prior to enrollment, oral steroids within 6 weeks of enrollment, omalizumab (Xolair®) within 6 months prior to enrollment, or who are currently using beta adrenergic blocking agents.
- Who have had any upper respiratory tract infections within six weeks prior to enrollment
- Who have been hospitalized or treated in the emergency room (unless the treatment involved the use of a bronchodilator only) for asthma within the last three years.
- Who have required nasal or sinus surgery, excluding surgery for a deviated septum within 12 months prior to enrollment.
- To avoid RV-16 inoculations in subjects with more restrictive lung volumes, those whose FVC is < 80% predicted will be excluded.
- Subjects who have had one or more night time awakenings caused by asthma symptoms and/or who have needed their SABA (albuterol) inhaler for asthma symptoms ≥4 days during the week before enrollment, or during the week before the inoculation with RV-16.
- Who are pregnant wish to become pregnant during the study, or who are nursing a baby.
- Who have a 5 pack/year history of smoking, or any smoking within the last 6 months.
- Who have a history of chronic illnesses, lung disease other than asthma, congenital heart disease, or immunosuppression.
- Subjects who are currently receiving allergen immunotherapy (IT), or who have received allergen IT within the last 2 years.
- Absolute neutrophil count (ANC) < 1500 cells/mm3 (or 1.5 K/uL) detected during screening within 6 weeks of enrollment, or when rechecked within 2 days of virus inoculation.

Control subjects

Criteria for exclusion will include those:

- Who test positive for serum neutralizing antibodies at a serum dilution of $\geq 1:4$ to the strain of virus (currently RV-16) which will be used for the experimental infection.
- Who have had any upper respiratory tract infections within six weeks prior to enrollment.
- Who have required nasal or sinus surgery, excluding surgery for a deviated septum within 12 months prior to enrollment.
- Who are pregnant, wish to become pregnant during the study, or who are nursing a baby.
- Who have a 5 pack/year history of smoking, or any smoking within the last 6 months. Who have a history of chronic illnesses, lung diseases, congenital heart disease, or immunosuppression.

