Subjects will be initially screened via IBR-HSR protocol #12656 to qualify for enrollment in this study. Those who qualify and sign the consent form for the study can participate and will start the Run-In period of home monitoring 7 days before virus inoculation (day -7). The samples collected and tests done at enrollment (day -7) and just prior to inoculation with RV-16 will be used to establish baseline values (see below). Note: Day -7 identifies the day of enrollment which can also be scheduled in the morning one day before (i.e., day -8) or in the morning afterward (day -6) to fit the schedule of those who participate. If possible, however, scheduling the initial enrollment visit on day -7 is optimal and strongly encouraged.

- 1. Initial Enrollment Visit (in the morning between 7 AM and noon on Day -7)
 - Urine pregnancy test
 - An administered past medical history questionnaire
 - Physical Exam focusing on eyes, ears, nose, heart and lungs
 - Nasal Wash
 - After the nasal wash an additional nasal specimen will be obtained by using a ASI Rhino-Pro® nasal mucosal curette plastic device to do a light scrapping along the inferior turbinate of each nostril to collect epithelial cells. This will be done using a headlight and a disposable nasal speculum to spread the nares (Bionix) to enhance visibility of the turbinates.
 - Spirometry
 - Expired Nitric Oxide
 - Impulse oscillometry. Impulse oscillometry is a means of assessing respiratory system impedance in a spontaneously breathing patient. In practice, the subject breathes through a mouth seal in line with a loudspeaker that generates a pulse wave lasting 0.1 second that is transmitted down the airways. By generating sound waves of varying frequencies throughout the respiratory cycle, the instrument can evaluate airway patency and resistance at many different levels within the respiratory tree during normal breathing. While spirometry is relatively insensitive with regards to the small airways, oscillometry may provide us with the precision required to evaluate these airways that are more likely to be involved in asthma, particularly during a RV infection. Repeated measurements do not alter pulmonary function, it is suitable for bedside measurements, and it is not effort dependent.

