Nose bleed	Occurs frequently Cocurs infrequently X Occurs rarely Frequency unknown
Nasal Bleeding	Occurs frequentlyOccurs infrequentlyX_Occurs rarely Frequency unknown

3.2 List by bullet format a summary of safety tests/procedures/observations to be performed.

- Adequate screening including Pregnancy Testing
- Pulse Oximetry (should symptom exacerbations occur as noted in the Treatment Plan above, pg. 13)
- Physical Exams
- Spirometry
- Daily home symptom and FEV₁ monitoring.
- Physicians and/or nurses, or respiratory therapists from the University of Virginia Asthma and
 Allergic Diseases Center, or the Pediatric Respiratory Disease division will be on site in the hotel
 24/day for the duration of the subjects' hotel stay. The study team on site will provide monitoring of
 the study subjects and will be available as needed to the study subjects. In addition, epinephrine,
 albuterol, and oral steroids will be readily available to the member of the study team to use for
 treatment if necessary.

2.3 Under what criteria would an INDIVIDUAL SUBJECT'S study treatment or study participation be stopped or modified X At subject, PI or sponsor's request

V C(1 1 11 ('C(1 1' (1 1 ' 1 1

__X__Study procedures would stop if the subject had a serious adverse event deemed related to the study. See description of SAE's above..

X If, after inoculation with the RV-16 pool, two subjects experience severe asthma exacerbations requiring oral steroids for ≥ 5 days annually (during the spring or fall enrollments), or if 1 subject requires treatment in the ER with systemic steroids, or hospitalization at any time during the study. Among the last 46 asthmatic subjects challenged with RV, only one subject required intervention with a 5 day course of oral steroids, but did not require treatment in the ER or hospitalization (which has never occurred in our rhinovirus challenge studies). Because the exclusion criteria (see below) obviates the enrollment of subjects who have required treatment in the ER, or hospitalization during the last 3 years (or any intubation ever requiring management in an intensive care unit), we suspect that it is not likely that the above stopping rules will be encountered.

Page 35 of 50

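### Section 2.3 cites a lifetime bar on intensive-care intubation that neither asthma exclusion list contains, and the two lists give different immunotherapy intervals

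*Combined protocol and SAP*

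**What the plan says.** Section 2.3 of the Data and Safety Monitoring Plan sets out stopping criteria. One limb needs two subjects with severe exacerbations requiring oral steroids for at least 5 days. Another is met "if 1 subject requires treatment in the ER with systemic steroids, or hospitalization at any time during the study". The section then reports that, of the last 46 asthmatics challenged, one needed a 5-day oral steroid course and none needed the emergency room or hospital. It goes on to say that the exclusion criteria keep out people with emergency-room treatment "or hospitalization during the last 3 years (or any intubation ever requiring management in an intensive care unit"), and concludes: "we suspect that it is not likely that the above stopping rules will be encountered".

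The asthma exclusions are printed twice, in the Study Synopsis and in the body under Inclusion/Exclusion Criteria. On severe asthma history, both lists exclude those "hospitalized or treated in the emergency room (unless the treatment involved the use of a bronchodilator only) for asthma within the last three years". Neither mentions intubation or intensive care.

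On allergen immunotherapy, the synopsis excludes current recipients and those "who have received allergen IT within the last 3 years". The body excludes current recipients and those "who have received allergen IT within the last 2 years".

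The synopsis also requires that a participant be "eligible for participation based on results of screening procedures conducted by protocol number 20100686 at VCU and IRB# 12656 at UVA". The enrollment visit includes "An administered past medical history questionnaire".

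**The concern.** A safety section names a protection, and the lists that staff would apply at enrollment do not contain it. The intubation clause is a lifetime bar, which makes it different in kind from the three-year rule beside it. If it is meant to be in force, the printed criteria do not enforce it. If it is not, section 2.3 describes the enrolled population as lower risk than the lists guarantee. Every subject receives live rhinovirus, and one limb of the section 2.3 rule is met by a single event, so the criteria that screen for past severe asthma need to be the ones the safety argument cites.

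The immunotherapy conflict is a separate matter of eligibility. The same person gets opposite answers depending on which list is used, so staff cannot follow both lists and enroll that person.

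**Working it through.** No sample size, power or error-rate figure is involved, so the check is a side-by-side reading of the current text.

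| Item | Section 2.3 | Synopsis, asthma exclusions | Body, asthma exclusions |
|---|---|---|---|
| Hospital or emergency-room treatment for asthma | 3 years | 3 years, bronchodilator-only emergency treatment exempt | 3 years, same exemption |
| Intubation ever, managed in intensive care | Stated as an exclusion | Absent | Absent |
| Allergen immunotherapy | Not mentioned | 3 years | 2 years |

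**Intubation.** The criterion is cited once and appears in 0 of the 2 asthma lists. The all-subjects and control lists do not contain it either, and the parenthesis in section 2.3 is the only mention of intubation in the text supplied. Section 2.3 refers the reader to criteria below it, but no exclusion list follows; both lists come earlier. Let *u* be the years since an intubation for asthma.

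- *u* ≤ 3: in practice caught by the hospitalization criterion in both lists.
- *u* > 3: barred according to section 2.3, not barred by either list.

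The gap is therefore confined to intubations more than three years ago.

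**Other criteria that might close the gap.** Most describe current or recent status: ACT above 19, short-acting beta-agonist use over 4 weeks, controller drugs in the past month, oral steroids within 6 weeks, omalizumab within 6 months, night awakenings and rescue use in the week before enrollment or inoculation, and the FEV1 and FVC limits. The longest look-back for a severe asthma event is three years. No printed criterion asks about lifetime history.

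**Immunotherapy.** Let *t* be the years since the last immunotherapy. The synopsis excludes *t* ≤ 3 and the body excludes *t* ≤ 2. The lists disagree for 2 < *t* ≤ 3, a window of 3 − 2 = 1 year.

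**Experience cited beside the exclusions.** Oral steroids: 1/46 = 2.2%. Emergency room or hospital: 0/46. The documents do not say whether any of the 46 had a remote intubation, so these figures do not show what would happen in such a subject.

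**The case against.** The strongest reply has three parts.

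First, the expectation about the stopping rules does not rest on the intubation clause alone. The sentence just before it gives the record in 46 asthmatics. The safety background adds roughly 100 to 120 mild asthmatics challenged at various centers, with no reported emergency-room visit or hospitalization, and its own argument uses only the three-year look-back. This stands. A reader might infer that the safety conclusion collapses without the intubation bar; the documents do not support that. The clause is one stated reason alongside experience, in a sentence the authors hedge.

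Second, the bar may be applied elsewhere. Eligibility depends on screening protocols that are not supplied, a medical history is taken at enrollment, and the treatment guidelines refer to a Complete Clinical Protocol that is also not supplied. This stands as a limit on the practical effect. It does not reconcile the printed text. Section 2.3 points to the exclusion criteria and not to another protocol, and where the lists do rely on screening results, as for prick skin tests, they still print the criterion and cite the source.

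Third, subjects have mild asthma on bronchodilators only, and staff with rescue drugs are on site around the clock. Both lower the risk. On-site cover, however, lasts for the hotel stay of about three and a half days, while follow-up runs to day 28.

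A reader might also infer that someone with past near-fatal asthma would be inoculated, or that the immunotherapy conflict endangers subjects. Nothing in the documents shows either.

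**Conclusion.** Both mismatches are in the current text and should be corrected. The intubation bar that section 2.3 cites is missing from both asthma lists, which leaves intubations more than three years ago unaddressed by the printed criteria. The immunotherapy intervals differ by one year; this is an eligibility inconsistency with no demonstrated safety effect.

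The size in subjects cannot be given, because the documents offer no basis for estimating how many of the 18 planned asthmatics have either history. Counting the years of life outside the three-year window would not fill that gap, since it is not a risk. No endpoint, analysis, sample size, power figure or stopping threshold is affected.

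Confidence is high on the text and moderate on the practical effect. The latter assumes that the screening protocols, the history questionnaire and the Complete Clinical Protocol do not already carry the bar, which cannot be checked here.

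**What to change.** Add the intubation clause of section 2.3, in the sponsor's own words, to the asthma exclusions in both the synopsis and the body, and correct the section 2.3 pointer so that it leads to those lists. If the screening protocols already contain the bar, restating it takes one line.

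Use one immunotherapy interval in both lists. Three years is the safe default because it satisfies both, unless the sponsor confirms two.

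The cost is amendment wording in two lists and a very slight narrowing of the eligible pool: people with a remote intensive-care intubation and, if three years is kept, those between 2 and 3 years past immunotherapy.

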2.5 What are the criteria for breaking the blind/mask? X_NA - Not blinded/masked
2.6 How will subject withdrawals/dropouts be reported to the IRB prior to study completion? X IRB-HSR continuation status form
3. Adverse Event / Unanticipated Problem Recording and Reporting
3.1 Will all adverse events, as defined in section 1.1, be collected/recorded? Yes
3.2 How will adverse event data be collected/recorded? _XPaper AE forms/source documents

Page 36 of 50

Protocol Version Date: 10/18/2016; Version13.0; NIH # U01-UVA-03

3.3. How will AEs be classified/graded?

__X__ All adverse events whether or not listed in the NCI-CTCAE will be graded on a scale from 1 to 5 according to the following standards in the NCI-CTCAE manual (A semi-colon indicates 'or' within the description of the grade.):

Grade 1 = Mild; asymptomatic or mild symptoms; clinical or diagnostic observations only; intervention not indicated.

Grade 2 = Moderate; minimal, local or noninvasive intervention indicated; limiting age-appropriate instrumental ADL (preparing meals, shopping for groceries or clothes, using the telephone, managing money, etc).

Grade 3 = Severe or medically significant but not immediately life-threatening; hospitalization or prolongation of hospitalization indicated; disabling; limiting self care ADL (bathing, dressing and undressing, feeding self, using he toilet, taking medications, and not bedridden).

Grade 4 = Life-threatening consequences; or urgent intervention indicated.

Grade 5 = Death related to AE

3.4 What scale will the PI use when evaluating the relatedness of adverse events to the study participation?

X The PI will determine the relationship of adverse events to the study using the following scale:

Related: AE is clearly related to the intervention
Possibly related: AE may be related to the intervention
Unrelated: AE is clearly not related to intervention

3.5 When will recording/reporting of adverse events/unanticipated problems begin?

X_After subject begins study drug/ device placement/intervention /study-related procedure/specimen collection

3.6 When will the recording/reporting of adverse events/unanticipated problems end?

_X__Subject completes intervention and follow up period of protocol. An adverse event will be followed until any of the following takes place: a) it is resolved, b) participant is stable, c) a minimum of 30 days after participant is terminated from the study and the NIAID Medical Officer and the Principal Investigator determine that follow-up is complete. If an abnormal value or result from a clinical or laboratory evaluation (e.g., a radiograph, an ultrasound, or an electrocardiogram) is determined to be an AE (refer to National Cancer Institute's Common Terminology Criteria for Adverse Events Version, Version 4.0, May 2009), then the

Page 37 of 50

evaluation that produced the value or result can be repeated until the value or result returns to normal, or the result can be explained, or the usual standard of care does not require further follow-up, and the participant's safety is not at risk.

3.7 How will Adverse Events, Unanticipated Problems, Protocol Violations and Data Breaches be reported? Complete the table below to answer this question

Type of Event	To whom will it be reported:	Time Frame for Reporting	How reported?
Any internal event resulting in death that is deemed possibly related to (caused by) study participation (Note: An internal event is one that occurs in a subject enrolled in a UVa protocol.)	IRB-HSR & NIAID MO: [name],	Within 24 hours	IRB Online and phone call www.irb.virginia.edu/
Internal, Serious, Unexpected adverse event	IRB-HSR	Within 7 calendar days from the time the study team received knowledge of the event. Notification to the NIAID MO – within 1 calendar day from the time the study team received knowledge of the event. Timeline includes submission of signed hardcopy of AE form.	IRB Online www.irb.virginia.edu/
Unanticipated Problems that are not adverse events or protocol violations This would include a Data Breach.	IRB-HSR & NIAID MO	Within 7 calendar days from the time the study team received knowledge of the event.	Unanticipated Problem report form. http://www.virginia.edu/vpr gs/irb/HSR_docs/Forms/Re porting_Requirements- Unanticipated_Problems.d oc)

Protocol Violations (The IRB-HSR only requires that MAJOR violation be reported, unless otherwise required by your sponsor, i applicable.) Or Enrollment Exceptions	IRB-HSR & NIAID MO	Within 7 calendar days from the time the study team received knowledge of the event.	Protocol Violation and Enrollment Exception Reporting Form http://www.virginia.edu/vpr gs/irb/hsr_forms.html
Data Breach	The UVa Corporate Compliance and Privacy Office, a ITC: if breach involves electronic data-	As soon as possible and no later than 24 hours from the time the incident is identified. As soon as possible and no later than 24 hours from the time the incident is identified. IMMEDIATELY.	UVa Corporate Compliance and Privacy Office- [contact] ITC: Information Security Incident Reporting procedure, http://www.itc.virginia.edu/sec
	UVa Police if breach includes such things as stolen computers.		urity/reporting.html Phone- [contact]

	UVa PI HELI	O IND/IDE	
Life-threatening and/or fatal unexpected	FDA	Within 7 calendar days of	Form FDA 3500A
events related or possibly related to the use	events related or possibly related to the use the study team learning of		
of the investigational agent.		the event	
Serious, unexpected and related or possibly related adverse events	FDA	Within 15 calendar days after the study team receives knowledge of the event	Form FDA 3500A (MedWatch) or narrative
For Device Studies: Unanticipated adverse device effects (internal or external)	FDA	Within 10 working days of the study team receiving knowledge of the event	Form FDA 3500A (MedWatch) or narrative
All adverse events	FDA	Annually	IND annual report

4 1	TT	•11	41	1 .	4 1	4	1	11	4	1/	1	
4.	HOW Y	will	tne	endpoi	nt a	ลเล	ne (COIL	ecte	n/r	ecoro	ıea

X Source documents

5. Data and Safety Oversight Responsibility

